7.2 End of Study Definition

A participant is considered to have completed the primary study if they have completed all phases of the study including return of equipment to study team and the 1 week follow-up to assess the family's overall experience. Additionally, participants will be given the option to participate in 6-month/12-month follow-up. After these sessions are completed and the medical records are obtained, a participant is considered to have completed the follow-up study visits.

8.0 SUBJECT SELECTION

8.1 Inclusion & Exclusion Criteria

Inclusion Criteria

1. Aged between 8 years 0 days and 21 years 365 days

2. Children who have hemiparetic cerebral palsy with a history of perinatal brain bleed/stroke
3. Receptive language function to follow two-step commands
4. Able to give informed assent along with the informed consent of the legal guardian. If the participant is 18-21 (with the capacity to consent), they must be able to give informed consent.
5. Intentional about representing the sub-population of children with CP who experience intellectual disability (at least 2/10 participants with mild intellectual disabilities will be recruited)
6. ≥ 10 degrees of active motion at the metacarpophalangeal joint
7. Children who have had surgeries, which may influence motor function e.g.- tendon transfer, will be included, yet surgical history will be documented and included in any publication within a participant characteristics table.

Exclusion Criteria

1. Inaccessibility to internet and a working computer/laptop/device.
2. Implants
3. Neoplasm
4. Metabolic Disorders
5. Epilepsy
6. Seizure within two years preceding the study
7. Acquired Traumatic Brain Injury
8. Pregnancy
9. Indwelling metal or incompatible medical devices
10. Evidence of skin disease or skin abnormalities
11. Botulinum toxin or Phenol block within [six-months] preceding the study
12. Disorder of Cellular Migration and Proliferation

8.1.1 Inclusion/Exclusion Criteria for Optional 6 Month/12-month Follow-up

To be eligible for the optional 6-month/12-month follow-up, participants must have previously participated in the primary study and have access to a reliable internet connection and a functioning computer, laptop, or mobile device. Apart from these requirements, there are no other exclusion criteria.

8.2 Vulnerable Populations

Vulnerable populations excluded from participation in the study

1. Pregnant women/fetuses/neonates for the primary study. If participants become pregnant after participating in primary study, they may participate in the 6- and 12-month follow up sessions..
2. Non-English speakers.

3. Those unable to read (illiterate).
4. Employees of the researcher.
5. Students of the researcher.
6. Individual or group that is approached for participation in research during a stressful situation such as emergency room setting, childbirth (labor), etc.
7. Individual or group with a serious health condition for which there are no satisfactory standard treatments.
8. Individual or group with a fear of negative consequences for not participating in research (e.g. institutionalization, deportation, disclosure of stigmatizing behavior).
9. Any other circumstance/dynamic that could increase vulnerability to coercion or exploitation that might influence consent to research or decision to continue in research.

This study will enroll children because the research is critical to advance the care and rehabilitation of children with CP and presents minimal risk to the children. From enrollment in past studies, we have found children with a CP diagnosis may be receiving physical or occupational therapy. If a child is receiving any concurrent therapies, all of the therapies will be documented. Data collected will inform future larger clinical trial evaluating the efficacy of at-home combined tDCS and rehabilitation in CP. Integrating tDCS as an adjuvant modality to telerehabilitation has the potential to enhance the efficacy of telerehabilitation therapies and offers a novel approach for remote intervention access, particularly relevant to reduce treatment cost and burden in case of limited access to clinic or hospital facilities. To further minimize risks to children, a trained study team member will supervise for safety concerns during all tDCS sessions in person and permission will also be obtained from a parent/guardian. If the participant is 18-21 years of age and has the capacity to give consent (adult child), permission will be obtained from the participant and the parent as participation is required from both parent and child.

When in contact with potential participants between the ages of 18-21, we will determine if they have the capacity to consent (10.3.3 Adults Unable to Consent).

We will NOT enroll participants whose capacity to consent may fluctuate throughout their involvement in the study. Using videoconferencing, a lab member will instruct the participants on how to perform tDCS stimulation. This will include 1 day of practice with inactive tDCS, 1 day of sham stimulation, and 3 days of active tDCS.

We are studying children and young adults aged 8-21 who have hemiparetic cerebral palsy with a history of perinatal brain bleed/stroke. The knowledge to be gained from this study will be beneficial in developing protocols for continuing pediatric rehabilitation therapy during mandated Stay-At-Home directives and other access restrictions (e.g., rural communities). We anticipate minor adverse events as listed in the adverse events section below. During the testing session, behavioral and environmental strategies will be shared, as needed, with the parent/caregiver for all children to optimize tolerance and completion of each session. These may include but are not limited to predictable routines, a visual timer, distraction techniques and child-friendly descriptive language. As we are a pediatric laboratory with experienced pediatric researchers, clinicians and trainees, comprehensive efforts have been made to ensure that our procedures are developmentally appropriate to both participant and family. Recruitment materials, study information, and conversations are tailored to a pediatric population. Participant-specific study materials are provided before participation in testing sessions, and age-appropriate adaptations for each procedure/test are used. Our team has created videos that help explain the research and videos specific to the procedures of this study will be shared with families.

8.3 Lifestyle Considerations

Not applicable

8.4 Subject Identification

8.4.1 Self-Identification

Since study subjects will need to be in an age range between 8 years to 21 years potential subjects will not be able to self-identify. However, parents/legal guardians of children that meet inclusion criteria could 'self-identify' due to their parental role. Participants who are between 18-21 years of age can self-identify as long as they have consent capacity. Parents/legal guardians, and participants 18-21 with consent capacity can respond to Institutional Review Board (IRB)-approved recruitment efforts, such as web postings, posters/flyers, radio or TV ads, newspaper ads, mass mailings, email blasts, etc. IRB-approved screening scripts, eligibility questionnaires, and email response templates will be utilized when communicating with parents/legal guardians of potentially eligible subjects who respond to these recruitment methods. Information collected from the parents/legal guardians of potential subject is to be limited to protect the potential subject's privacy, and information collected from potential subjects who fail pre-screening will be destroyed. Indirect recruitment materials and response communications will not contain subject health information.

8.4.2 Pediatric Neuromodulation Laboratory Database

We will use our own database from participants who have previously participated in our studies and have signed consent to be contacted for this study.

8.5 Subject Recruitment

A total of 10 subjects will be recruited. Several recruitment strategies are as detailed below. The phone screening script will be used in response to calls or emails from potential subjects.

Based on recruitment in previous studies in this population performed by our lab, we expect that about 75% of our sample of children will reside within the state where the laboratory exists, i.e., Wisconsin. The remaining participants will be recruited from the greater Midwestern and Western regions. We have experienced exceptional participation (increase in overall enrollment from initial inquiries in our studies from 9% to 14% over the last 5 years), retention (100% in 3 studies of 50 total children), and adherence (99.8%) in our trials of over 539 total visits. 7 participants from the pilot study in our lab expressed interest for future studies and agreed to be re-contacted for participation. Recruitment will take place immediately after IRB approval and continue for 12 months. The baseline diagnosis for children who have hemiparetic cerebral palsy with stroke/brain bleeds has been established and documented through previous involvement in our studies; however, we will gather medical records for current medical status to confirm there are no changes in medical status.

8.5.1 Email

Children who have hemiparetic cerebral palsy with a history of perinatal brain bleed or stroke will be recruited from our database of previous participants. We will contact the list of previous participants in our laboratory studies who have agreed to be re-contacted and expressed interest in participation in future studies. We will recruit participants through email and establish a time to screen via telephone.

8.5.2 Self-Identify

Self-identify: Parents/legal guardians of children who meet inclusion criteria could self-identify in response to IRB-approved recruitment materials, such as web posters/flyers, social media posts, emails, mailings, etc. Anyone who sees information about this study may pass the information onto potentially eligible families, who may choose to contact the study team. Relevant local and national groups will be provided with IRB-approved recruitment materials and language to be posted on their

websites and social media platforms. Participants 18-21 with capacity to consent are able to self-identify in response to any IRB approved recruitment materials.

8.5.3 Flyers

Flyers announcing that volunteers are needed for the study will be posted or sent out to various specialty clinics or schools serving our population of interest. Several key details of the study will be included in the flyer (key eligibility criteria, number and length of visits, location of study site, type of remuneration) along with a call back number for people to call in case they are interested.

8.5.4 Health Records

We will work with UW ICTR's Clinical Research Data Service (CRDS) to identify eligible patients at within UW Health.

Additionally, study team with electronic medical record access may search patient lists made available to them as part of their research access to identify potential subjects at recruiting sites for study eligibility evaluation. The research team will conduct further prescreening of individual records to identify potential participants.

8.5.5 Mailing Opt-Out Letters

Study team with research access to the electronic medical record system will use appropriate ICD codes to identify potential participants. Families at UWHealth will be mailed the opt-out letter. This letter informs families that a study team member will be calling within two weeks to discuss the study and inquire about the family's interest. Upon receipt of the letter, the family may choose to email the study team to express interest in the study or opt-out of contact.

8.5.6 Calling

Within 2 weeks of mailing the opt-out letter, a study team member will reach out to the potential participant family. Up to three call attempts will be made by the study team. If call goes to voicemail, the approved voicemail phone script will be used.

8.5.7 Waisman Registry

We will work with the Intellectual & Developmental Disabilities Research Registry at the Waisman Center. The individuals enrolled in this registry may be contacted to potentially participate in this study. The research team will set up a time to screen the participants if they are interested in participating in this study.

8.5.8 Clinical Practice

Hospital/clinic care providers at institutions serving our target population may identify potential participants during routine clinical care based on inclusion/exclusion criteria. They may provide IRB-approved recruitment materials to patient families and invite them to contact the study team if they are interested in learning more.

8.6 Remuneration and Retention Strategies

Based on our previous experience in pediatric non-invasive stimulation and infant stroke studies, we will utilize the following retention tools:

- Once eligibility has been confirmed, we will contact the parents/legal guardians or adult child participant and their parent to schedule a conversation in-person or a video chat to answer any additional questions and to introduce our team and put a face with a name.
- Throughout the five consecutive days of the study, we will check in with the parents/legal guardians or adult child participant to answer questions and provide any pertinent information.
- We will contact the parents/legal guardians or adult child participant via phone one week before their visits to answer any questions/concerns.
- We have a dedicated laboratory study phone number which we share with parents/legal guardians/adult child participants, and to which we attend regularly.

- We will invite parents/legal guardians/adult child participants to be on our mailing list to receive biannual Pediatric Neuromodulation Lab newsletters for updates.
- A consistent point of contact will be maintained with parents/legal guardians/adult child participants, from recruitment to study completion, to establish rapport and build a positive relationship between the family and research team.
- A thank-you letter with a summary of participation will be sent to parents/legal guardians/adult child participants after completion of all sessions. Upon completion of the 5 sessions, each family will receive \$100 for participation. If the study is stopped due to an adverse event or because the participant wants to stop for any reason, they will receive compensation at a prorated rate based upon the number of sessions completed. Participants will receive \$50 for each additional optional follow-up visit they complete. This will total to an additional \$100 for completing both the 6-month and 12-month follow-up visits.

8.7 Early Termination and Withdrawal

Families are free to withdraw from participation in the study at any time upon request.

The Principal Investigator (PI) may discontinue or withdraw a subject from the study for the following reasons at his/her discretion:

- Legal guardian/parent of the child voluntarily withdraw from the study
- Participant death
- Pregnancy
- Subject non-compliance with study requirements (e.g., study intervention non-compliance)
- If any clinical adverse event (AE), laboratory abnormality, or other medical condition or situation occurs such that continued participation in the study would not be in the best interest of the subject
- If the subject is no longer an appropriate candidate for participation
- There is evidence of progressive disease or unacceptable toxicity
- Subject unable to complete the 5 sessions within two weeks

Participants withdrawn from study will be replaced, and the details surrounding the circumstances for withdrawing the participant from the study will be reported, with no identifiers included. Data collected up to the point of withdrawal will be kept and used for analysis. Participants who withdraw from the study will be given the opportunity to be involved in the 6-month/12-month follow up study visits.

If the study ends prior to the study completion, all scheduled participants and families will be notified, and study sessions will be terminated. All research investigators on the study will be notified. The funding agency will also be notified.

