3.0 STUDY SUMMARY

3.1 Synopsis

Full Title	Remotely Monitored Transcranial Direct Current Stimulation in Children with Cerebral Palsy
Short Title	Pediatric Brain and Movement
Protocol Number	[HS IRB]
ClinicalTrials.gov Identifier & Summary	This study is being performed to determine the safety, tolerability and feasibility of remotely monitored transcranial direct current stimulation for children with cerebral palsy.
Number of Site(s)	This study is being done at one site: The University of Wisconsin Madison.
Main Inclusion Criteria	
 Children with hemiparetic cerebral palsy with a radiologically confirmed perinatal brain bleed/stroke Ability to follow 2-step commands Aged between 8 years 0 days and 21 years.
Main Exclusion Criteria	
 Inaccessibility to internet and a working computer/laptop/device Neoplasm Presence of metal implants Epilepsy History of seizure within 2 years preceding the study
Objective(s)	
Primary Objective
 
 To assess safety and tolerability of remotely monitored tDCS using our safety survey and optional 6-month/12-month follow up 
Secondary Objectives
 
 To evaluate the quality, ease and comfort of in-home device set-up. To evaluate the quality of tDCS stimulation.
Endpoints	
Primary Endpoint
 
Adverse events survey (pre, during, and post stimulation on sessions 1-5) and Box and Blocks test (pre and post stimulation sessions 2-5) will assess possible adverse effects.
 
Secondary Endpoints
 
 Setup speed SMARTscan™ electrode contact quality
Study Design	This is an exploratory pilot open label trial that will assess the safety and feasibility of active tDCS in the home setting under caregiver and remote investigator supervision and direction, with a study safety monitor in the home on days when there is an active device present. An optional 6 month/12-month follow up session will be completed to to assess Box and Blocks scores and medical status since r participation in the primary study.

IND or IDE Number	Abbreviated IDE requirements apply for Non-Significant Risk Device
Study Intervention	Participants will receive 20 minutes of 1.5 mA transcranial direct current stimulation (tDCS) for three consecutive days.
Total Number of Subjects	A total of 10 subjects will be recruited.

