Study Population	Male and females aged 8 to 21 with established diagnosis of hemiparetic cerebral palsy with a history of perinatal stroke/brain bleed who are US residents.
Statistical Methodology	Adverse event reporting frequency (% of total participants enrolled) and tolerability will be compared to pediatric tDCS studies performed within the laboratory setting and administered by trained research personnel. This data is publicly available in the form of published trials from our group and other groups. For participants in the 6-month/12-month follow-up, we will monitor for any change in motor function by comparing box and blocks scores from the primary study and 6-month/12-month study follow up visits. We will also assess current medical status by pursuing updated medical records.
Estimated Subject Duration	The duration of the study for each subject is approximately 5 days.
Estimated Enrollment Period & Study Duration	Study enrollment and follow-up will occur over 10 months with the total expected duration of the trial to be 12 months.

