9.2 Study Procedural Intervention(s) Description

9.2.1 Administration of Procedural Intervention

Active tDCS stimulation will be delivered to the participants during sessions 3-5 of the study after participants have been evaluated and cleared for quality set-up of the tDCS montage. A trained study team member will interact virtually with the caregiver to activate the tDCS stimulation device while a safety monitor team member will be located in person to supervise any safety concerns.

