10.3.4 Enrollment

A research subject will be defined as "enrolled" in the study when they meet the following criteria:

- The subject has been consented and assented by study staff.
- The subject and study staff have completed all screening documentation.
- The PI has verified that the subject meets all of the inclusion criteria.
- The PI has verified that subject meets none of the exclusion criteria.

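### Adverse-event frequency is a percentage of all enrolled, so children lost and replaced before active stimulation can lower the active-stimulation rate

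*Combined protocol and SAP*

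**What the plan says.** All of these places are in the combined protocol and SAP.

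- **Denominator.** 3.1 Synopsis, Statistical Methodology: "Adverse event reporting frequency (% of total participants enrolled) and tolerability will be compared to pediatric tDCS studies performed within the laboratory setting".
- **Enrolment.** 10.3.4 requires consent and assent ("The subject has been consented and assented by study staff"), completed screening documentation, and the principal investigator's check of the eligibility criteria. No study session is required.
- **Exposure.** 9.2.1: "Active tDCS stimulation will be delivered to the participants during sessions 3-5 of the study". Session 1 uses a mock device and session 2 is sham (10.2.1). Active stimulation also depends on the set-up having been judged adequate.
- **Replacement.** 8.7: "Participants withdrawn from study will be replaced". The listed withdrawal reasons include adverse events, unacceptable toxicity, non-compliance and failure to fit the five sessions into two weeks. None is exempt from replacement, and there is no cap.
- **What happens to withdrawn children.** The same sentence of 8.7 adds that "the details surrounding the circumstances for withdrawing the participant from the study will be reported, with no identifiers included", and the next says "Data collected up to the point of withdrawal will be kept and used for analysis".
- **Target.** 3.1: "A total of 10 subjects will be recruited". The text does not say whether this means enrolled, actively stimulated or completing.
- **Completion.** Aim 2 (6.1) expects participants to complete repeated active sessions, and 7.2 says when a participant has completed the primary study. Neither gives a completion rate or a denominator.

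**The concern.** Safety and tolerability are the primary objective, and the only planned comparison of adverse-event frequency is with stimulation given in the laboratory. The rate of interest for that comparison is the rate among children who received active stimulation. The stated denominator is wider. It takes in every child who passed screening, including any who left after consent, after the mock session or after sham.

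Replacement makes this matter. Without it, a child lost early would reduce the number exposed and the shortfall would be plain. With it, the exposed group is topped up to 10 while the lost children remain in the denominator. If they reported no event, the active-stimulation rate falls for a reason unrelated to how well stimulation was tolerated, and it falls in the reassuring direction.

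A second, separate gap concerns completion. Because total enrolment can exceed 10, the reader needs to know over whom completion is counted, and the text does not say.

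**Working it through.** The documents give no event rate, margin or calculation behind the 10, so there is no figure to reproduce. The check uses direct proportions.

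**Inputs.** From the documents: target of 10 (3.1); all-enrolled denominator (3.1); active stimulation from session 3 (9.2.1); past retention of 100% in 50 children (8.5 and 10.13). Assumed, because the documents give neither: w = 1, 2 or 3 children lost before session 3 with no event and replaced, so that 10 are actively stimulated; and, for illustration, x = 3 or 4 children with an active-stimulation event.

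**Step 1: dilution.** Rate over exposed = x/10. Rate over enrolled = x/(10 + w). Relative fall = 1 − 10/(10 + w) = w/(10 + w), whatever x is.

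| w | Relative fall | x = 3: exposed → enrolled | x = 4: exposed → enrolled |
|---|---|---|---|
| 1 | 1/11 = 9.1% | 30.0% → 3/11 = 27.3% | 40.0% → 4/11 = 36.4% |
| 2 | 2/12 = 16.7% | 30.0% → 3/12 = 25.0% | 40.0% → 4/12 = 33.3% |
| 3 | 3/13 = 23.1% | 30.0% → 3/13 = 23.1% | 40.0% → 4/13 = 30.8% |

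**Step 2: no events seen.** The one-sided 95% upper bound is 1 − 0.05^(1/n). With n = 10 it is 25.9%. With n = 11, 12 or 13 it is 23.8%, 22.1% or 20.6%. The bound tightens although no further child was actively stimulated.

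**Step 3: sampling error, for scale.** The exact 95% interval for 3/10 is 6.7% to 65.2%. The shifts for x = 3 are 2.7, 5.0 and 6.9 percentage points.

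**Step 4: how many losses are plausible.** Retention of 50/50 is compatible with a withdrawal probability q of up to 1 − 0.05^(1/50) = 5.8% (one-sided 95%) or 1 − 0.025^(1/50) = 7.1% (two-sided).

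- Chance of at least one withdrawal among the first 10, 1 − (1 − q)^10: 45% or 52%.
- Expected replacements to reach 10 completers, 10q/(1 − q): 0.6 or 0.8.
- At assumed q of 10% or 20%: 1.1 or 2.5 expected replacements.

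These figures count withdrawals at any stage. Losses before session 3 are only a part of them.

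**Step 5: children withdrawn after an event.** Suppose v children are actively stimulated, have an event, withdraw and are replaced, and 3 of the 10 completers also have an event. Under 8.7 the rate is (3 + v)/(10 + v): 4/11 = 36.4%, 5/12 = 41.7% or 6/13 = 46.2% for v = 1, 2 or 3, against 30.0% in completers alone. These children raise the reported rate.

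**Step 6: completion under two possible denominators.** With 10 completers and 1, 2 or 3 replaced withdrawals, completion over all enrolled is 10/11 = 90.9% (exact 95% interval 58.7–99.8%), 10/12 = 83.3% (51.6–97.9%) or 10/13 = 76.9% (46.2–95.0%). Over the final 10 alone it is 10/10 = 100% (69.2–100%). The text selects neither.

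**The case against.** **Withdrawals are not hidden.** Section 8.7 keeps and analyses data up to withdrawal and reports the circumstances. A reader might infer that intolerant children disappear from the safety record. They do not: Step 5 shows that they push the adverse-event rate up if the stated rules are followed. This stands, and it confines the dilution to children lost early without an event.

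**Completion is not stated to be perfect by construction.** A reader might infer that replacement guarantees 10 completers out of 10. No section counts completion over the final 10. The only denominator the plan names, for adverse events, is all enrolled, and on that basis a replaced child prevents 100%. This stands too. What remains is that the denominator is unstated, so the final-10 reading is not excluded.

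**Early leavers can contribute events.** The adverse-event survey runs in sessions 1 to 5 (10.2.5), and sham itself includes brief current ramps (10.2.1). Children seen only at mock or sham may therefore report tingling or discomfort. This stands: an all-session rate is less clearly diluted than the active-stimulation rate. The synopsis does not say which one it means.

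**The size is small.** Past retention was complete in 50 children, and the interval around 3/10 dwarfs the shift. This stands as a limit on size. It does not justify a denominator that includes children who were never at risk.

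**Other text may settle it.** The table of contents lists 12.2, 12.3 and 12.5, but their bodies are not in the text available for review. An analysis set may be defined there. The synopsis rule would then still need to agree with it.

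**Conclusion.** The point holds in a limited form. Under the synopsis wording, enrollees lost before session 3 without an event lower the active-stimulation adverse-event rate by a relative 9%, 17% or 23% for 1, 2 or 3 such losses alongside 10 actively stimulated children. The counts are assumptions. The retention history makes 0 or 1 the likelier outcome, although it comes from earlier studies and may not carry over to home sessions.

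It would go too far to say that replacement and the denominator together bias the results in the trial's favour. The two issues involve different children, events in withdrawn children are retained, and the completion denominator is undefined rather than wrongly defined. Nor can it be said that the comparison with laboratory studies will necessarily be flattering, because the denominators of those studies are not given in the documents.

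**What to change.** 1. In the 3.1 Synopsis, replace the all-enrolled percentage for active-stimulation events with the frequency among participants who started at least one active session.
2. Report mock-session and sham-session events separately, each over the participants who started that session, so that early withdrawals for discomfort stay visible. Pooling sham and active starters in one denominator would not do, because children lost after sham would still dilute the active-stimulation rate.
3. Define completion as completing all three active sessions. Report it over all who started session 1 and, separately, over all who started session 3. Count replaced participants as non-completers and add their replacements to the denominator.
4. State whether 10 means enrolled, exposed or completers.

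The cost is wording only. The session-by-session surveys and attendance already supply the data. Reported rates may look slightly less favourable.
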